#### **f. Expected outcomes, possible problems and solutions.**

The main expected outcomes of the study will be:

- clinical improvement in AD and bvFTD patients following network recalibration
- identification of surrogate biomarkers of network recalibration

Possible problems:

- Few patients recruited: Low risk. The IRCCS-FBF is a leading centre in the study of AD and related disorders, with hundreds of outpatients seen every year.
- High drop out: Medium risk. Patients will undergo an intensive research program, which might lead to a high drop out rate. To overcome this problem, we will enlarge the patient recruitment pool to neighbouring clinical centers in Brescia and elsewhere.

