#### **Clinical assessment**

Each patient will undergo a clinical and neuropsychological evaluation to assess symptoms and cognition at baseline (before tDCS session, T0) and follow-up (after the tDCS sessions, T1; and 6 months after tDCS treatment, T2). Patients will also undergo biological samples collection (CSF at T0, blood samples at T0, T1, T2) to assess the effect of tDCS on inflammatory measures (optional sub-study).

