#### **Outcome measures**

We will test whether the stimulation of AD- and bvFTD-disrupted networks improves patients clinical condition.

PRIMARY efficacy parameters will be:

- change in scores at T1 compared with T0 for clinical and behavioural scores in AD and bvFTD patients

SECONDARY outcome measures will be:

- change in scores at T1 compared with T0 for cognitive performance in AD and bvFTD patients
- change in scores at T2 compared with T0 for clinical, behavioural, and cognitive performance in AD and bvFTD patients

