### **Aim3**

To elucidate the mechanisms underlying network recalibration, in vivo biomarkers of structural and functional networks connectivity will be collected off-line. Each subjects will undergo an MRI scan on a 3T scanner at the UO3. The following sequences will be collected:

- resting-state functional MRI (rs-fMRI), to assess DMN and SN functional connectivity
- arterial spin labelling (ASL), to measure DMN and SN brain perfusion
- diffusion tensor imaging (DTI), to measure DMN and SN structural connectivity
- structural MRI, for the routine assessment of cortical and hippocampal atrophy

Scan will be collected at baseline (T0, prior to tDCS experiment), after completion of the tDCS sessions (T1), and after 6 months (T2). The subjects included in this analysis will be those recruited for AIM1 and AIM2 (20 AD and 20 bvFTD).

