### **Statistical analysis**

Sample size for this pilot study (n=10 subjects for each experimental group) has been determined on the basis of previous tDCS (Cotelli et al., 2011) and rs-fMRI studies (Lorenzi et al., 2011; Pievani et al., Alzheimer's Dementia 2014) of the Consortium.

Paired t-tests will be used to compare pre-treatment (T0) *versus* post-treatment (T1, and T2) variables in each treatment group (AD and bvFTD).

Correlations between clinical/cognitive changes and imaging biomarkers will be assessed with Pearson's correlation coefficient.

Two-sample t-tests will be used for cross-sectional comparisons of clinical/cognitive scores between paradigm 1 and 2 (i.e. network stimulation *versus* network inhibition) in the experimental groups and to evaluate differences in clinical, cognitive, and neuroimaging measures between the experimental groups and controls at baseline.

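### The plan meets possible high drop-out only with wider recruitment and tests change only in patients with both visits, leaving an avoidable completer bias, mainly at T2

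*Combined protocol and SAP*

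**What the plan says.** Section f (*Expected outcomes, possible problems and solutions*) lists high drop-out as a medium risk and gives the reason: "Patients will undergo an intensive research program, which might lead to a high drop out rate". The one remedy is that "we will enlarge the patient recruitment pool to neighbouring clinical centers in Brescia and elsewhere".

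The *Statistical analysis* part of section e covers change from baseline in one sentence, which opens "Paired t-tests will be used to compare pre-treatment (T0" and goes on to name T1 and T2 as the later visits, within each treatment group. On size it says: "Sample size for this pilot study (n=10 subjects for each experimental group) has been determined on the basis of previous tDCS", with further reference to earlier imaging studies. It states no drop-out allowance.

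Under Aim 1, *Outcome measures*, the primary parameter is "change in scores at T1 compared with T0 for clinical and behavioural scores in AD and bvFTD patients". A secondary one is "change in scores at T2 compared with T0 for clinical, behavioural, and cognitive performance in AD and bvFTD patients". T1 follows the two weeks of sessions, and T2 comes six months after treatment. Aim 2 uses the same outcomes.

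The document defines no analysis population, no rule for missing outcomes and no sensitivity analysis. It does not say how added recruits relate to patients who have left.

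**The concern.** A paired t-test needs both values. A patient seen at T0 and T1 but not at T2 contributes nothing to the T2 result, although the T1 score says something about how that patient was doing. The T1 and T2 tests may therefore rest on different patients, and each estimates the change among those who stayed.

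Wider recruitment answers a shortage of patients. It does not answer the loss of outcomes. If patients who do worse tend to leave, the mean change among completers is too favourable, and further recruits subject to the same selection give the same shifted mean. The shift is toward improvement, the direction the plan hopes for. No concurrent untreated group would reveal it, since the healthy controls are assessed only at baseline. At T2 it bears on whether any benefit appears to last six months.

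**Working it through.** **The plan's own figures.** There are four experimental groups of 10 (AD and bvFTD under each paradigm), 40 patients in all. The plan gives no drop-out rate, SD, effect size, alpha or power, so n = 10 cannot be reproduced. Every rate and correlation below is an assumption.

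**Assumptions.** Changes from T0 are in SD units, positive meaning better. The true mean change is zero, drop-out before T2 is d = 30%, and testing is two-sided at 5%. A normal liability decides who stays. Its correlation r with the observed T1 change is 0.3, 0.5 or 0.7. The T1 and T2 changes correlate 0.6. Given the T1 change, leaving does not depend further on the T2 change.

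**Step 1: shift among those who stay.** With c the 30% point of the standard normal, c = −0.524 and φ(c) = 0.348, so φ(c)/(1 − d) = 0.348/0.70 = 0.497. The mean T1 change among stayers is r × 0.497, and the mean T2 change is 0.6 × r × 0.497.

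**Step 2: effect on the paired t-test.** Rejection of a true null with 10 completers, from the noncentral t distribution with noncentrality bias × √10 and 9 degrees of freedom:

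| r | T1 change, stayers (SD) | T2 completer bias (SD) | Two-sided rejection, n = 10 |
|---|---|---|---|
| 0 | 0 | 0 | 5.0% |
| 0.3 | 0.149 | 0.089 | 5.7% |
| 0.5 | 0.248 | 0.149 | 7.1% |
| 0.7 | 0.348 | 0.209 | 9.1% |

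Direct simulation, which allows for the smaller spread among completers, gives 5.8%, 7.1% and 9.2% for the last three rows.

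**Step 3: other drop-out rates.** At 20%, φ(c)/(1 − d) = 0.350, so the T2 bias runs from 0.6 × 0.3 × 0.350 = 0.06 to 0.6 × 0.7 × 0.350 = 0.15 SD. At 40% the factor is 0.644 and the range is 0.12 to 0.27 SD.

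**Step 4: what replacement does.** Nothing in Step 1 depends on the number recruited, so topping up to 10 completers leaves the bias as it was. It only makes a biased mean more likely to reach significance. For example, if leaving is tied directly to the change being tested (30% drop-out, correlation 0.5), a false finding of benefit, nominally 2.5%, occurs in about 8.4% of trials with 7 completers and 11.2% with 10.

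**Step 5: what using T1 does.** In simulations of four groups of 10, the T2 mean was estimated from all T1 changes with one T1-to-T2 slope shared across groups. Its bias was at most 0.002 SD in every row of the table. Its standard error was about 0.37 SD, against 0.37 to 0.39 SD for the completer mean.

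**Step 6: precision alone.** The 95% half-width for a mean change is t(n − 1)/√n. It is 2.262/√10 = 0.72 SD for 10 patients and 2.447/√7 = 0.92 SD for 7. That loss occurs even when leaving is unrelated to outcome.

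**The case against.** The strongest case against runs as follows.

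- **The plan does not predict high drop-out.** It calls it a medium risk and says it might occur. The cause it names is the burden of the programme. If burden is unrelated to outcome, r = 0 and there is no bias. This stands, and it is why the size is conditional.
- **The larger harm, at the primary outcome, is not one that a model cures.** A reader might infer that the primary T1 result is inflated by 0.15 to 0.35 SD, with 7 to 17% false rejection, and that a mixed model removes this. Those figures arise when leaving depends on the patient's own unseen change. A patient lost before T1 has only a T0 score, so the model has little to work with. Nor does the document show that such drop-out will occur over two weeks of sessions. The objection stands: those figures cannot justify the model.
- **Replacement does not enrich the sample with responders.** A reader might infer that it does. Step 4 shows that the completers' mean is the same with or without it. The plan also does not say that recruits take leavers' places; it only enlarges the pool.
- **Filling missing changes with zero is no safeguard.** The background section describes progressive degeneration, so no change is a favourable value. Suppose the true T2 change is −0.30 SD, drop-out is 30%, and leaving correlates 0.3 with that change. Completers give −0.30 + 0.149 = −0.15, and zero-filling gives 0.7 × (−0.15), about −0.11, further from the truth. With uninformative leaving it turns an unbiased −0.30 into −0.21.
- **A mixed model at this size needs its details fixed.** This is fair. Covariance structure and degrees of freedom matter with 10 per group and should be written down.

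The gap itself remains: no analysis set, no missing-data rule, and a test that discards observed T1 data when T2 is missing.

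**Conclusion.** The point holds in a limited form. The plan names drop-out as a risk, answers it only with recruitment, and uses a test that estimates change in those who stayed. The repairable harm is mainly at T2, a secondary outcome. It is 0.09 to 0.21 SD of bias, with about 6 to 9% rejection of a true null instead of 5%, if 30% leave and leaving follows the observed T1 change under the stated correlations. It is zero if leaving is unrelated to outcome. Using T1 brings it to about zero at no material cost in precision.

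A reader might infer that a lasting six-month effect could be created by drop-out alone. Bias of this size, in groups of 10, does not support that. For the primary T1 outcome the realistic gains are a defined analysis set, reported drop-out and a sensitivity analysis. This is an inexpensive improvement that should be made, not a flaw that invalidates the trial.

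**What to change.** In *Statistical analysis*, replace the paired t-tests with the following.

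1. **Model.** Fit one mixed model for repeated measures per outcome, with T0, T1 and T2 scores as responses and group × visit as fixed effects. Fit the four groups of 10 together, with a shared unstructured covariance and Kenward–Roger degrees of freedom. That is 4 × 3 = 12 means and 6 covariance parameters from 40 patients. Report the T1−T0 and T2−T0 contrasts for each group.
2. **Analysis set.** Include every patient who starts tDCS.
3. **Recruitment.** State that extra recruits are added to patients who left, not put in their place, and that leavers' data stay in the analysis.
4. **Reporting.** Give drop-out by group and visit.
5. **Sensitivity.** Use a delta adjustment at both T1 and T2, setting missing changes progressively worse than the model predicts. With 30% missing, a penalty of δ lowers a group's mean change by 0.30δ, so it is easy to show how large δ must be before a conclusion changes. This is needed at T1 in particular, because the model cannot correct drop-out before T1 that depends on the unseen T1 score.

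The cost is revised wording and slightly more analysis work, with no new data. The model assumes that data are missing at random given observed scores and, as specified, that all groups share one covariance matrix.

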#### **C. Significance and innovation**

This will be the first intervention targeting networks clearly linked to AD and bvFTD pathophysiology. The majority of stimulation studies for AD patients target task-specific networks, e.g. the dorsolateral prefrontal cortex (DLPFC) (NCT01746498 trial; Cotelli et al., 2011). Conversely, the present project will target disease-specific networks, and we expect that this approach will be more effective to modify the disease course.

Secondly, no previous study has attempted to recalibrate bvFTD networks. This study will be the first to a treatment option specific for these patients.

The main innovations of this pilot project will be:

- innovative disease-modifying treatments for AD and bvFTD patients (AIM1)
- potentially minimally invasive treatments (AIM2)
- better understanding of the neuronal mechanisms underlying brain damage and repair (AIM3)

#### **D. Description of complementary and synergy research team**

The project will bring together three research groups sharing a common and solid expertise in the study of brain connectivity in patients with dementia. In addition, these groups show complementary expertise in their own field: UO1 (Lab. of Epidemiology, Neuroimaging and Telemedicine, IRCCS Fatebenefratelli, Brescia) has a well documented expertise in the assessment of disease biomarkers with imaging techniques; UO2 (Neuropsychology Lab, IRCCS Fatebenefratelli, Brescia) has wide experience in the application of tDCS for the treatment of AD; and UO3 (Neuroradiology Unit, Azienda Ospedaliera Universitaria Integrata Verona) in the development of methods for the study of brain connectivity. The track record of collaboration between these research lab is well-documented (Frisoni

et al., 2007, 2008; Canu et al., 2011; Lorenzi et al., 2011) and will be further amplified through the integration of these levels of expertise.

### **F. Timeline/Deliverables/Payable Milestones**

**Months 1-29:** Implementation of the clinical study (baseline assessment, T0)

**Months 1-29:** tDCS sessions

**Months 2-30:** Implementation of the longitudinal study (T1)

**Months 7-36:** Implementation of the longitudinal study (T2)

### **G. Milestone Mo 18**

**M1:** Successful implementation of the clinical study (First 2 patients completing T0 assessment; Month 1)

**M2:** Successful implementation of paradigm 1 (First patient completing tDCS sessions; Month 1)

**M3:** Successful implementation of paradigm 2 (First patient completing tDCS sessions; Month 1)

**M4:** Successful implementation of the longitudinal study (First patient completing T1 assessment; Month 2)

**M5:** Successful implementation of the longitudinal study (First patient completing T2 assessment; Month 8)

### **H. Milestone Mo 36**

**M1:** Recruitment of targeted patient group size (Last patient completing T0 assessment; Month 29)

**M2:** Completion of the clinical study (Last patient completing T2 assessment; Month 36)

**M3:** Project validation (Report of statistical analysis; Month 36)
